## 14. ANALYSES OF TREATMENT PATTERN AND HEALTHCARE RESOURCE UTILIZATION/COST

### 14.1. Treatment Pattern analyses

Treatment pattern analyses will be performed in Full Population. The treatment patterns and their grade are defined in Table 4.

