| Protocol Activity   | Screen/Baseline | Study visit     |   |                 |   |   |
|---|-----------------|-----------------|---|-----------------|---|---|
|   |                 | X  | - | X  | - |   |
| Monthly CAT   | X  | -               | - | X  | - | - |
| Blood biomarkers (inclusive of serum sRAGE, CC16, IP-10, HbA1c) | X               | -               | - | X               | X | X |
| Sputum cytology                                    | X               | -               | - | X               | X | X |
| Sputum microbiome                                  | X               | -               | - | X               | X | X |

CAT=COPD assessment test, COPD=Chronic Obstructive Pulmonary Disease, HRCT=High-resolution computed tomography, EW=Early Withdrawal, EXACT=EXAceration of COPD Tool; SGRQ-C=St.George's Respiratory Questionnaire for COPD. CAPTURE=COPD Assessment in Primary Care to Identify Undiagnosed Respiratory Disease and Exacerbation Risk

1. Exacerbation visits only apply to subjects included in the Biomarker & Digital sub-cohort. Moderate exacerbations are defined as COPD exacerbations that require either systemic corticosteroids (intramuscular (IM), intravenous, or oral) and/or antibiotics. Severe exacerbations are defined as COPD exacerbations requiring hospitalization or result in death.
2. Informed consent must be conducted at the screen visit prior to performing any study procedures.
3. For COPD participants only;
4. When a trimonthly telephone interview overlaps a clinical visit, the COPD exacerbation assessment, COPD medication and treatment questionnaires will be completed at the clinic visit. A month is defined as 30 days in this study.
5. Data collection of COPD exacerbation assessment, COPD medication and treatment are not required for the healthy control participants.
6. CT scan should only be performed at withdrawal visit if the last study CT performed was more than a year ago. Inspiratory and expiratory HRCT scans are required at Visit 1 and Visit 4, while only inspiratory scan will be conducted on exacerbation visit. The CT scan for an exacerbation visit should only be performed if the last study CT scan performed was more than 14 days.
7. Pre-and post- bronchodilator values of spirometry test will be collected at each site visit.

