#### **10.2.5. Treatment Pattern and Healthcare Resource Utilization/Cost**

For COPD-related treatment, the following endpoints will be described using frequency and percentage:

- Each type of treatment for COPD patients
- Initiation of maintenance treatment
- Switches to another maintenance treatment
- Addition of other maintenance treatment
- Stepping up to triple therapy
- Discontinuation of treatment

COPD-related and non-COPD healthcare resource utilization and cost will be described with appropriate descriptive statistics:

- Total medical cost, pharmacy cost, and other costs
- Number of outpatient visit and cost
- Number of emergency visit and cost
- Number of hospitalization, length of stay, and cost
- Treatment of exacerbation and cost

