
2. Characterise stable disease and exacerbation phenotypes in China through assessment of blood biomarkers, lung microbiome and radiological features of COPD
	
Main cohort:
 
 
• Plasma fibrinogen and high-sensitivity C-Reactive Protein (hsCRP)
 
• Differential blood cell count (e.g. eosinophils, neutrophils) and haemoglobin
 
 
Additional for sub-cohort
 
 
• Blood biomarkers including but not limited to Serum interferon- <math>\gamma</math> -inducible protein -10 (IP-10), soluble Receptor for Advanced Glycation End Products (sRAGE), Club cell protein (CC16) and HbA1c
 
• Sputum microbiome as assessed by molecular methods
 

Research Questions & Objectives	Endpoints
	
 
• Sputum total differential cell counts and percentage (e.g. total cell count, the counts and percentage of eosinophils and neutrophils)
 
• CCI
 

3. Characterise treatment pathways and healthcare resource utilization and costs in COPD
	
 
• Frequency of treatment with COPD medications; Treatment patterns at the time of study entry and during the study period
 
• Count of outpatient visits, emergency visits, hospitalizations (overall and COPD-specific)
 
• Direct medical costs associated with COPD medications and COPD disease management
 
• Insurance coverage and patient out-of-pocket payment
 

4. Test the feasibility of integrating electronic health records, electronic clinical outcome assessments (eCOA) and physical activity data to support application of digital data analytics (DDA) platform in China studies (e.g. direct digital data capture and integration)
	NA

\*Moderate exacerbations are defined as COPD exacerbations that require either systemic corticosteroids (intramuscular (IM), intravenous, or oral) and/or antibiotics. Severe exacerbations are defined as COPD exacerbations requiring hospitalization (including intubation and admittance to an ICU) or result in death.

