## 4. ANALYSIS POPULATIONS

**Table 2. Summary of Study Populations**

Population	Definition / Criteria	Analyses Evaluated
All Screened	
The All Screened Population will consist of all participants who sign the ICF to participate in the clinical trial.
 
Participants in this population will be used for screen failure summary.
	
 
• Study Population
 

Full	The Full Population will consist of all subjects (except subject PPD ) who are enrolled in the study and attend Visit 1, and not withdraw informed consent.	
 
• Study Population
 
• Disease Progression Analyses
 
• Phenotypic Analyses
 
• Treatment Pattern and Healthcare Resource Utilization/Cost
 
• Safety Analyses
 

Sub-cohort	Sub-cohort is a subset of Full population. Subjects who are enrolled in the Biomarker & Digital sub-cohort and who provided at least one additional sub-cohort assessment.	
 
• Study Population
 
• Disease Progression Analyses
 
• Phenotypic Analyses
 
• Treatment Pattern and Healthcare Resource Utilization/Cost
 
• HRCT analysis
 

HRU	HRU is a subset of Full population. The following sites are not feasible to capture data by HIS, thus the patients enrolled from the following sites will be excluded from HRU analysis: 238160, 238222, 237965, 237971, 238155.	
 
• Treatment Pattern and Healthcare Resource Utilization/Cost
 

[figure not shown]
\*: Subject PPD cannot be categorized into either of the study arms (COPD patients, Chronic Bronchitis patients or Healthy Control), thus excluded from the Full population.

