## 5. CONSIDERATIONS FOR DATA ANALYSES AND DATA HANDLING CONVENTIONS

### 5.1. Number of Participants

A total of 2,000 participants are planned to be enrolled, consisting of 1,700 participants with COPD, 180 with chronic bronchitis but without fixed airflow limitation, and 120 never smoker healthy control. Specifically, COPD subjects will be classified using the GOLD grades I – IV (i.e. mild, moderate, severe and very severe). To better understand the disease progression of early stage COPD, i.e. GOLD I and II grades, COPD participants will be recruited in the following manner: GOLD I: 700, GOLD II: 700, GOLD III: 200, GOLD IV: 100 ([Figure 1](#)[Error! Reference source not found.](#)).

[figure not shown]
Figure 1 Study Population Schematic

More assessments will be conducted among the 400 Biomarker & Digital sub-cohort participants who will be all recruited from selected Type A hospitals. The sub-cohort consists of 50 never smoker healthy control, 100 chronic bronchitis (N never smoker: 25), 100 GOLD I (N never smoker: 25), 100 GOLD II (N never smoker: 25) and 50 GOLD III participants (N never smoker: 20) ([Figure 2 Sub-cohort Population Schematic](#)). In GOLD I-III grades, certain number of COPD participants with previous exacerbation history (i.e. exacerbators) will be recruited (target number of subjects are as follows - GOLD I: 60 exacerbators, GOLD II: 60 exacerbators, GOLD III: 30 exacerbators). Further, a proportion of those who are maintenance inhaler treatment naïve

will be recruited, aiming for: 10 participants who are maintenance inhaler treatment naive will be recruited among exacerbators and non-exacerbators in each GOLD I, II, III groups respectively (Figure 2). All patient population sizes are approximate and allow +/- 10% for feasibility.

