**Table 4 Treatment Pattern Definition**

Treatment pattern	Treatment pattern Grade	Details in Treatment or the Combination
Naive	0	No any COPD treatment
Stop	0	Only COPD treatment records before 90 days from the first visit
LAMA	1	LAMA
LABA	1	LABA
ICS/LABA	2	ICS/LABA, or Combination 2, at the same time check: "ICS"+"LABA"
LAMA/LABA	2	LABA/LAMA, or Combination 2, at the same time check: "LABA"+"LAMA"
Triple(open)	3	When "Triple (open) =1": Combination 1, at the same time check: "ICS/LABA"+"LAMA", or Combination 2, at the same time check: "ICS/LABA"+"LABA/LAMA", or Combination 3, at the same time check: "ICS"+"LABA/LAMA", or Combination 4, at the same time check: "ICS"+"LABA"+"LAMA"
Triple(closed)	3	ICS/LABA/LAMA

Descriptive summary of treatment pattern for each visit will be provided with frequency and percentage for the following subgroups: gender, age (<50, 50-59, 60-69, 70-80, >80), smoking status, employment status, Type of Hospital (Type A/B), GOLD grade, Previous Exacerbation status (Yes/No), Hospitalization in preceding year (Yes/No), Presence of chronic bronchitis (Yes/No). All the concomitant medication records collected on Visit 1 within 90 days before the will be considered as baseline and the post-baseline visits contains records collected from the date of last visit to the current visit, e.g. Visit 2 refers to the record from the date of Visit 1 +1 to date of Visit 2. The descriptive summary will be provided by the treatment pattern shown in Table 4.

A shift table will be provided to show the change (step up, stable, switch, step down or stop/missing, treatment naive) of treatment patterns for each visit compared with previous visit and visit 4 compared with baseline, with number of participants in the study, number and percentage of participant in the pre-defined category. The summary will be based on all the post-baseline concomitant medication collected from the date of last visit to the current visit, e.g. Visit 2 refers to the record from the date of Visit 1 +1 to date of Visit 2, and the changes of treatment pattern are defined as:

- Step up: the treatment pattern grade become larger than previous visit ;
- Switch: the treatment pattern changed within a same grade (except grade 0)
- Stable: the treatment pattern remain the same (except grade 0)
- Step down: participants receive treatment and the grade goes down compared with the previous visit;
- Stop/missing: No treatment record in the period

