**CONFIDENTIAL**

Protocol Activity		Screen/Baseline	Study visit				
	CAT (Phone Call)	Trimonthly Phone Call 					
Healthcare resource utilization and cost		-	X	X	X	X	X
Assessments							
COPD exacerbation assessment (on site visit) 		-	X	X	X	X	X
COPD exacerbation assessment (Phone Call) 		Trimonthly Phone Call 					
COPD medication and treatment (on site visit) 		X	X	X	X	X	X
COPD medication and treatment (Phone Call) 		Trimonthly Phone Call 					
Death		-	X				
Serious Adverse Event assessment 			X	X	X	X	X
Lab							
Blood Draw for e.g. fibrinogen/HsCRP/Cell count		X	-	-	X	X	X
Sub-cohort only							
Lung HRCT scan 		X	-	-	X	X	X
Daily steps		X 	-	X 	-	-	-
Evening diary (EXACT plus additional questions)		X 	-	X 	-	-	-
Monthly CAT		X 	-	X 	-	-	-
Blood biomarkers (inclusive of serum sRAGE, CC16, IP-10, HbA1c)		X	-	-	X	X	X
Sputum cytology 		X	-	-	X	X	X
Sputum microbiome 		X	-	-	X	X	X

CAT=COPD assessment test, COPD=Chronic Obstructive Pulmonary Disease, HRCT=High-resolution computed tomography, EW=Early Withdrawal, EXACT=EXAcerbation of COPD Tool; SGRQ-C=St.George's Respiratory Questionnaire for COPD.

1. Exacerbation visits only apply to subjects included in the Biomarker & Digital sub-cohort. Moderate exacerbations are defined as COPD exacerbations that require either systemic corticosteroids (intramuscular (IM), intravenous, or oral) and/or antibiotics. Severe exacerbations are defined as COPD exacerbations requiring hospitalization or result in death.
2. Informed consent must be conducted at the screen visit prior to performing any study procedures.
3. For COPD participants only;
4. When a trimonthly telephone interview overlaps a clinical visit, the COPD exacerbation assessment, COPD medication and treatment questionnaires will be completed at the clinic visit.
5. Data collection of COPD exacerbation assessment, COPD medication and treatment is not required for the healthy control participants.
6. CT scan should only be performed at withdrawal visit if the last study CT performed was more than a year ago. Inspiratory and expiratory HRCT scans are required at Visit 1 and Visit 4, while only inspiratory scan will be conducted on exacerbation visit.

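### SAP 14.1 sets the treatment-pattern tables in the Full Population, so healthy controls and chronic bronchitis participants are pooled into percentages meant to describe COPD patients

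*SAP*

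**What the plan says.** **Target.** SAP 2.2, Objective 3: "Characterise treatment pathways and healthcare resource utilization and costs in COPD". Protocol 10.2.5 opens its list of treatment endpoints with "Each type of treatment for COPD patients", and section 9.1 of the appended RAP names the same endpoint.

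**Population.** SAP 14.1: "Treatment pattern analyses will be performed in Full Population". SAP Table 2 defines that population as all subjects, apart from one who could not be classified, "who are enrolled in the study and attend Visit 1, and not withdraw informed consent". SAP 5.1 gives planned enrolment as "consisting of 1,700 participants with COPD, 180 with chronic bronchitis but without fixed airflow limitation, and 120 never smoker healthy control".

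**Categories.** SAP Table 4 assigns Naive (grade 0) to anyone without COPD treatment, whatever their diagnosis. The shift table defines "Stop/missing: No treatment record in the period". It also lists a treatment-naive category but does not define it. Its Stable and Switch categories exclude grade 0.

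**Display.** The subgroups in 14.1 include gender, age, smoking status, employment, hospital type and GOLD grade. No split by arm is specified, and SAP 5.4 sets no by-arm default.

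**Data.** The 14.1 tables are built on concomitant-medication records. Separately, footnote 5 to Protocol Table 1 says "Data collection of COPD exacerbation assessment, COPD medication and treatment are not required for the healthy control participants". SAP Appendix 2 carries the same footnote.

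**The concern.** The population in 14.1 is wider than the question it serves. SAP 2.1, which lists changes from the protocol, does not mention the widening. Elsewhere the SAP narrows the group when it means to: 6.4 limits COPD history to COPD patients, 7.1 limits exacerbations to COPD and chronic bronchitis, and 13.1 limits phenotypes to COPD patients. A programmer following 14.1 as written would include everyone.

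A healthy control with no inhaler then meets the definition of Naive. In the shift table, a participant at grade 0 in consecutive periods cannot be Stable, so the only defined category left is Stop/missing. That person is displayed alongside patients who stopped a treatment.

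At stake are the overall shares for naive, for each inhaled class and for each type of change. The smoking-status comparison is also affected, because every healthy control is a never smoker (Protocol 6.1) and the distortion falls on one side only.

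**Working it through.** **Plan's own figures.** 1,700 + 180 + 120 = 2,000, and 700 + 700 + 200 + 100 = 1,700 for GOLD I–IV. Both agree with SAP 5.1.

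**Inputs**
- Group sizes: SAP 5.1.
- Never-smoker cap: 30% in each GOLD grade and in chronic bronchitis (Protocol 5.2). This gives 0.30 × 1,700 = 510 and 0.30 × 180 = 54.
- Healthy controls: 120, all never smokers (Protocol 6.1).
- p, the naive share among COPD patients: not in the documents. Assumed 30, 40 or 50%, and equal in ever and never smokers.
- Healthy controls take no COPD inhalers: assumed.

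**Overall share, chronic bronchitis treated like COPD**

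Shown share = (1,880p + 120)/2,000 = 0.94p + 0.06.

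**Overall share, upper bound with all chronic bronchitis participants untreated**

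Shown share = (1,700p + 300)/2,000 = 0.85p + 0.15.

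| True p in COPD | Chronic bronchitis as COPD | Upper bound |
|---|---|---|
| 30% | 34.2% | 40.5% |
| 40% | 43.6% | 49.0% |
| 50% | 53.0% | 57.5% |

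**Never-smoker column at the 30% cap**

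Column size = 510 + 54 + 120 = 684. Healthy controls are 120/684 = 17.5% of it.

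With p = 40% and chronic bronchitis treated like COPD:
- never smokers: (564 × 0.40 + 120)/684 = 345.6/684 = 50.5%;
- ever smokers: 40%, because that column contains no controls.

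The gap of 10.5 points comes from the population alone.

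**Dependence on the chronic bronchitis assumption.** If all chronic bronchitis participants are untreated:
- never smokers: (510 × 0.40 + 54 + 120)/684 = 378/684 = 55.3%;
- ever smokers: (1,190 × 0.40 + 126)/1,316 = 602/1,316 = 45.7%.

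Both columns rise and the gap is 9.5 points, so the false contrast hardly depends on this assumption.

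**Fewer never smokers among patients.** With an assumed 15% (255 COPD and 27 chronic bronchitis), the column is 402 and controls are 120/402 = 29.9% of it. At p = 40%, with chronic bronchitis treated like COPD, it shows (282 × 0.40 + 120)/402 = 232.8/402 = 57.9%.

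**The case against.** **Uncollected data.** A reader might infer from footnote 5 that controls count as untreated because nobody asked them. The documents do not support that as the main cause. The 14.1 tables use concomitant-medication records, the schedule collects concurrent medications at V1–V4 from all participants, and respiratory medicines are included (Protocol 9.1 and 9.2.1). The footnote attaches to other rows of the schedule. Controls fall in grade 0 mainly because they have no COPD to treat. The denominator problem is the same either way.

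**A 15% dilution.** A reader might take all 300 participants without COPD as untreated. Nothing in the documents says that chronic bronchitis participants take no inhaled treatment, so 0.85p + 0.15 is only an upper bound.

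**Every table affected.** This is too broad. Rows by GOLD grade contain COPD participants only, and their counts sum to the COPD total. Exacerbation history is scheduled for COPD participants only, so how others enter that subgroup is unclear. The shift table lists a count of study participants, but the text does not say that this count is the percentage denominator.

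**Intent.** The objective and Protocol 10.2.5 both name COPD, so 14.1 may be loose wording. The table shells are not in the documents, and by-arm layouts are common elsewhere in the SAP. That possibility stands, but 14.1 is the operative instruction and does not say so. The COPD/non-COPD stratification in RAP 9.2 covers resource use only.

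**Importance.** The study is descriptive, and no test or FEV1 endpoint depends on these tables. They are, however, the treatment-pattern output for one of four objectives.

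**Conclusion.** The point holds. As written, 14.1 applies a population that does not match its objective, and the pooled naive share is too high for any COPD naive share below 100%, provided controls take no COPD inhalers. Overall the effect is modest: 3.0 to 4.2 points for p between 50% and 30%, with chronic bronchitis treated like COPD. The smoking-status comparison suffers more, with a spurious gap of about 10 points at p = 40% and the 30% cap. The gap widens if fewer patients are never smokers; the 15% illustration is an assumption, since the current protocol sets only a maximum.

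All sizes use planned numbers, which the plan calls approximate, and an assumed p. A reader might also infer that never smokers are the worst-affected stratum of all. That cannot be shown: they are more affected than the overall and ever-smoker figures, but the documents give no planned counts for the other strata. Protocol 5.4 notes a lack of data on phenotypes and progression in never smokers with COPD; it does not mention treatment, so it gives only indirect weight here.

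**What to change.** In SAP 14.1:
1. Restrict the Table 4 summaries, the subgroup tables and the shift table to COPD participants (GOLD I–IV) in the Full Population, and use COPD denominators for the percentages.
2. Show chronic bronchitis separately. A by-arm display with separate denominators would serve equally well.
3. Leave healthy controls out of any pooled percentage.
4. Define treatment naive in the shift table so that it is distinct from Stop/missing.

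If a wider population is really intended, list it in SAP 2.1 as a change from Protocol 10.2.5.

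The cost is a few sentences of SAP wording and a program filter. No new data are needed.

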**Table 4 Treatment Pattern Definition**

Treatment pattern	Treatment pattern Grade	Details in Treatment or the Combination
Naive	0	No any COPD treatment
Stop	0	Only COPD treatment records before 90 days from the first visit
LAMA	1	LAMA
LABA	1	LABA
ICS/LABA	2	ICS/LABA, or Combination 2, at the same time check: "ICS"+"LABA"
LAMA/LABA	2	LABA/LAMA, or Combination 2, at the same time check: "LABA"+"LAMA"
Triple(open)	3	When "Triple (open) =1": Combination 1, at the same time check: "ICS/LABA"+"LAMA", or Combination 2, at the same time check: "ICS/LABA"+"LABA/LAMA", or Combination 3, at the same time check: "ICS"+"LABA/LAMA", or Combination 4, at the same time check: "ICS"+"LABA"+"LAMA"
Triple(closed)	3	ICS/LABA/LAMA

Descriptive summary of treatment pattern for each visit will be provided with frequency and percentage for the following subgroups: gender, age (<50, 50-59, 60-69, 70-80, >80), smoking status, employment status, Type of Hospital (Type A/B), GOLD grade, Previous Exacerbation status (Yes/No), Hospitalization in preceding year (Yes/No), Presence of chronic bronchitis (Yes/No). All the concomitant medication records collected on Visit 1 within 90 days before the will be considered as baseline and the post-baseline visits contains records collected from the date of last visit to the current visit, e.g. Visit 2 refers to the record from the date of Visit 1 +1 to date of Visit 2. The descriptive summary will be provided by the treatment pattern shown in Table 4.

A shift table will be provided to show the change (step up, stable, switch, step down or stop/missing, treatment naive) of treatment patterns for each visit compared with previous visit and visit 4 compared with baseline, with number of participants in the study, number and percentage of participant in the pre-defined category. The summary will be based on all the post-baseline concomitant medication collected from the date of last visit to the current visit, e.g. Visit 2 refers to the record from the date of Visit 1 +1 to date of Visit 2, and the changes of treatment pattern are defined as:

- Step up: the treatment pattern grade become larger than previous visit ;
- Switch: the treatment pattern changed within a same grade (except grade 0)
- Stable: the treatment pattern remain the same (except grade 0)
- Step down: participants receive treatment and the grade goes down compared with the previous visit;
- Stop/missing: No treatment record in the period

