### **2.2.2. Additional information for other endpoints**

Treatment pattern will be analysed in baseline (up to 90 days prior baseline to baseline), 0-6m, 6-18m and 18-30m.

HRU data will be analysed in total and by season, as defined in [14.2](#) .

Unless otherwise specified, the other endpoints will be analysed by visits.

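### Unequal look-backs bias the treatment-pattern shift table toward step up among intermittent users, and its Stop/missing row pools stopping with absence of data

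*SAP*

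**What the plan says.** SAP section 14.1 gives two rules for the records that count. For baseline: "All the concomitant medication records collected on Visit 1 within 90 days before the will be considered as baseline" (a word is missing, but Visit 1 is clearly meant). For later visits: "the post-baseline visits contains records collected from the date of last visit to the current visit". SAP section 2.2.2 states the same periods: "Treatment pattern will be analysed in baseline (up to 90 days prior baseline to baseline), 0-6m, 6-18m and 18-30m".

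Table 4 grades the patterns from 0 to 3. Grade 0 holds Naive and also Stop, which is a participant whose only COPD treatment records are older than 90 days at the first visit.

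The shift table is produced "for each visit compared with previous visit and visit 4 compared with baseline". Its main rule is "Step up: the treatment pattern grade become larger than previous visit". The only category for stopping is "Stop/missing: No treatment record in the period". A treatment-naive category is listed among the changes but not defined there, and no rule says which pattern counts when several occur in one window.

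The analysis is run in the Full Population. Protocol section 10.2.5 lists initiation, switching, stepping up to triple therapy and "Discontinuation of treatment" among the outputs.

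**The concern.** A shift table is read as change within a participant. That reading needs the state to be measured in the same way at both ends. Here the later window is two or four times as long as the earlier one in three of the four comparisons, so a participant who uses treatment now and then is more likely to be seen as treated later, with no change in behaviour.

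The stop row has a different problem. A participant who attended and takes no treatment, one who was never treated, and one who has left the study can all satisfy the condition of having no treatment record in the period.

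Objective 3 asks for treatment patterns at entry and during the study. Step-up and discontinuation are among its outputs, and these are the cells affected. No other planned table corrects them.

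**Working it through.** The plan states no figure for the shift table, so there is none to reproduce. The one numerical input that can be checked is dropout: 525 completers / (1 - 0.25) = 700, as in Protocol Table 2.

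**1. Window lengths.** Protocol section 2 says "A month is defined as 30 days in this study". The periods in SAP section 2.2.2 are then 90 days (baseline), 180 (Visit 2), 360 (Visit 3) and 360 (Visit 4). Later-to-earlier ratios:
- Visit 2 vs baseline: 180/90 = 2
- Visit 3 vs Visit 2: 360/180 = 2
- Visit 4 vs Visit 3: 360/360 = 1
- Visit 4 vs baseline: 360/90 = 4

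**2. One record under each rule.** Take a participant whose only record is 100 days before the visit.
- At Visit 1 it lies outside 90 days: Stop, grade 0.
- At Visit 2 it lies inside 180 days: grade 1, 2 or 3.
- At Visit 3 or 4 it lies inside 360 days: grade 1, 2 or 3.

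A move from grade 0 to any higher grade is a step up. This needs no assumption about rates.

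**3. Size in a no-change model (assumed).** Let an intermittent user's records arise at a constant rate r per 360 days, with r from 1 to 6 as an assumed range. Then:
- P(w) = 1 - exp(-r × w/360), the chance of at least one record in w days
- false step-up = [1 - P(earlier)] × P(later)
- false stop = P(earlier) × [1 - P(later)]

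Example, r = 2, Visit 4 vs baseline: P(90) = 0.393 and P(360) = 0.865. False step-up = 0.607 × 0.865 = 52%. False stop = 0.393 × 0.135 = 5%.

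| Comparison | Windows (days) | False step-up, r = 1/2/4/6 | False stop, r = 1/2/4/6 |
|---|---|---|---|
| Visit 2 vs baseline | 90, 180 | 31/38/32/21% | 13/14/9/4% |
| Visit 3 vs Visit 2 | 180, 360 | 38/32/13/5% | 14/9/2/0.2% |
| Visit 4 vs Visit 3 | 360, 360 | 23/12/2/0.2% | 23/12/2/0.2% |
| Visit 4 vs baseline | 90, 360 | 49/52/36/22% | 8/5/1/0.2% |
| Any, equal look-back | 90, 90 | 17/24/23/17% | 17/24/23/17% |

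The percentages are of intermittent users, not of the cohort. With equal windows the two columns agree and net drift is zero.

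**4. The merged row.** Let s be the true stop share among those still followed and d the share lost. If those lost stay in the denominator, the row shows s + (1 - s) × d. Protocol section 10.1.3 plans for 25% dropout. At Visit 4:
- s = 0: 25%
- s = 10%: 0.10 + 0.90 × 0.25 = 32.5%
- s = 20%: 0.20 + 0.80 × 0.25 = 40%

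If dropout has a constant hazard (assumed), d is 5.6% at Visit 2 and 15.9% at Visit 3, and a true 10% appears as 15.0% and 24.3%.

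**The case against.** The strongest case against the point has four parts.

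- **Maintenance treatment is meant to be continuous.** A continuous user has records in every window and shows no artefact. The documents do not give the share of intermittent users, so the effect on the cohort is unknown. This stands, and it limits the size that can be claimed.
- **A longer window need not raise the grade of someone already treated.** A reader might infer that every grade rises with window length. That would require the highest pattern in the window to be assigned, and the SAP gives no such rule. If the latest pattern counts, the effect falls mainly on participants otherwise at grade 0. Table 4 also appears to require the components of open combinations to be taken together, so drugs used one after another need not become triple therapy. Both limits stand. The grade 0 artefact in step 2 remains under either rule.
- **The stop row is labelled for what it is.** It says missing as well as stop, completers of each visit are tabulated elsewhere (SAP section 6.1), and the number of participants in the study may mean those still followed. In that last case dropout does not inflate the row, so the figures in step 4 are an upper bound. The row still cannot supply the discontinuation output that Protocol section 10.2.5 names.
- **The study is mainly descriptive, with no formal inference.** This lowers the stakes, but a descriptive table still has to describe change and not the length of the window.

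A reader might also infer that unequal windows create false discontinuation. They tend to do the opposite: one record early in a 360-day window keeps a participant out of the stop row, so longer windows hide stopping.

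**Conclusion.** The point holds as two separate faults of definition.

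**Look-back.** Visit 2 vs baseline, Visit 3 vs Visit 2 and Visit 4 vs baseline are biased toward step up among intermittent users. Visit 4 vs Visit 3 is not biased. The direction follows from the stated rules alone. The size rests on an assumed constant record rate of 1 to 6 per 360 days with no true change: for Visit 4 vs baseline, 22-52% false step-up against 0.2-8% false stop.

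A reader might turn the growth in detection between windows into a fold increase in step-up. At r = 1 the chance of being seen as treated goes from 22.1% in 90 days to 63.2% in 360, a ratio of 2.9. That is a ratio of two detection probabilities. It is not the share of participants who move up, which is the within-person quantity in the table.

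**Merged row.** Stopping cannot be separated from absence of data. At the planned 25% dropout, a true 10% at Visit 4 would appear as 32.5% if dropouts stay in the denominator, and the inflation is smaller or nil if they do not.

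The SAP should be changed on both counts. Neither fault touches the lung-function or exacerbation analyses.

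**What to change.** In SAP section 14.1:

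- For the shift table, classify every visit on the same look-back, the 90 days up to that visit, and state one rule for a window that contains several patterns.
- Keep use over the whole inter-visit interval as a separate any-use table.
- Replace the Stop/missing row with three: previously treated and now no treatment; never treated; no visit or no data. SAP sections 8.2 and 8.3 already show missed visits as missing.
- Base percentages on participants with data at both visits compared, and say so.

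No new data are needed. Under Protocol section 9.2.1 medication is recorded at each clinic visit and at the three-monthly telephone interviews. The cost is SAP wording, one derivation and the table rows.

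Two losses should be accepted openly. Short courses early in an interval appear only in the any-use table. Equal windows also remove the net drift but not the noise: in the model above, 17-24% of intermittent users still move each way, so apparent stops among them rise from the 0.2-8% shown by the present Visit 4 vs baseline rule.
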